**SHORT TITLE/ACRONYM**

policymakers will share results and gather feedback. Evidence syntheses, policy briefings, and press releases will accompany publications, including an article for *The Conversation*.

All materials and code will be shared in high-impact journals and open-access repositories to promote reproducibility. Findings will be presented at international conferences (e.g., WILD28, IASCL27).

## **4 STUDY SETTING**

### **Study sites and design**

This is a **single-centre study** conducted at two closely linked settings within the same research infrastructure:

1. The **Neonatal Care Unit (NCU)** at the host NHS Trust.
2. The **Oxford Brookes University BabyLab (Centre for Psychological Research)**.

Together, these settings allow recruitment, exposure to the study environment, and developmental assessment to be carried out in a way that is appropriate, safe, and aligned with the research aims.

### **Access to participants**

- **Preterm infants** are identified and initially approached within the NCU by members of the clinical care team (research nurses). Families who express interest are then approached by the research team to provide full study information and obtain informed consent.
- **Full-term infants**, and potentially preterm infants receiving standard care, are identified through the Oxford Brookes BabyLab participant database. Families registered in the database are contacted when their child reaches the appropriate age and are provided with full study information before deciding whether to participate.

### **Activities at each site**

- **Neonatal Care Unit:**
  - Identification of eligible preterm infants by the clinical team.
  - Initial approach to families by research nurses.
  - Exposure to the study sound environment for participating infants during their NCU stay.
  - No additional clinical procedures beyond standard care.
- **Oxford Brookes BabyLab:**
  - Longitudinal behavioural testing of infants at multiple time points.
  - Parent-completed questionnaires assessing language and development.
  - Video monitoring during testing sessions for attention and safety purposes only.

**SHORT TITLE/ACRONYM**

**Appropriateness of the research setting**

The NCU is essential for addressing the research question, as it is the environment in which preterm infants experience altered auditory input compared to the womb. The BabyLab provides a controlled, infant-friendly setting with well-established methodologies for measuring early language and cognitive development. Together, these settings allow the research aims to be addressed comprehensively across early development.

**Site-specific requirements**

- Close collaboration with NCU clinical staff to ensure that all procedures are compatible with routine neonatal care.
- Secure storage facilities for consent forms and data within restricted-access areas.
- Access to quiet, infant-appropriate testing spaces within the BabyLab.

**Types of activity across sites**

- **NCU:** Identification, initial approach, parental recording procedures, and exposure during hospital stay.
- **BabyLab:** Recruitment via database, developmental testing, questionnaire administration, and follow-up.

This integrated study setting ensures that the research can be conducted safely, ethically, and in a way that directly addresses the study's aims.

## **5 SAMPLE AND RECRUITMENT**

### **5.1 Eligibility and Inclusion Criteria**

Preterm Group

1. Gestational age  $\geq 26$  and  $\leq 34$  weeks.
2. Absence of major cerebral damage (e.g., periventricular leukomalacia, intra-ventricular haemorrhage...).
3. No indication of visual or hearing impairment.
4. No family risks of developmental or language disorders.
5. From monolingual English-speaking families.

Full-term Group

1. Gestational age  $\geq 37$  weeks.
2. Absence of major cerebral damage (e.g., periventricular leukomalacia, intra-ventricular haemorrhage...).
3. No indication of visual or hearing impairment.

**SHORT TITLE/ACRONYM**

4. No family risks of developmental or language disorders.
5. From monolingual English-speaking families.

### **5.1.1 Exclusion criteria**

#### **Preterm infants**

- Infants will be excluded from the study if they meet any of the following criteria:
- Born before 26 weeks' gestation or after 34 weeks' gestation.
- Evidence of major brain injury or neurological damage, including but not limited to periventricular leukomalacia or intraventricular haemorrhage.
- Known or suspected hearing impairment or visual impairment.
- Presence of diagnosed genetic, neurological, developmental, or language disorders, or a known family history of developmental or language disorders that may affect language development.
- Infants from bilingual or multilingual households, or where English is not the primary language spoken to the infant at home.
- Medical instability or clinical concerns identified by the neonatal care team that would make participation inappropriate or place additional burden on the infant or family.

#### **Full-term infants**

- Infants will be excluded from the study if they meet any of the following criteria:
- Born before 37 weeks' gestation.
- Evidence of major brain injury or neurological damage, including but not limited to periventricular leukomalacia or intraventricular haemorrhage.
- Known or suspected hearing impairment or visual impairment.
- Presence of diagnosed genetic, neurological, developmental, or language disorders, or a known family history of developmental or language disorders that may affect language development.
- Infants from bilingual or multilingual households, or where English is not the primary language spoken to the infant at home.
- Any medical condition or clinical concern identified by the clinical or research team.

### **5.2 Sampling**

#### **5.2.1 Size of sample**

The study will include a total of **150 infants**, accounting for an estimated **20% attrition rate** due to the longitudinal nature of the research (10%) and participation in multiple experimental tasks (10%). This sample size ensures sufficient statistical power for comparisons across the three study groups.

The final sample will comprise:

- Preterm infants exposed to a womb-like auditory environment.
- Preterm infants receiving standard neonatal care.
- Full-term comparison infants.

**SHORT TITLE/ACRONYM**

Sample size calculations were informed by prior research on early speech perception and language development in preterm infants, which report medium to large effect sizes ( $d = 0.59\text{--}0.80$ ). Power calculations ( $\alpha = 0.05$ , power = 0.80) conducted using G\*Power (version 3.1) indicate that this sample size is adequate to detect meaningful group differences in language and cognitive outcomes. This sampling strategy directly addresses the study's aim of identifying whether early auditory experience influences language development trajectories.

### **5.2.2 Sampling technique**

A purposive sampling strategy will be used.

- Preterm infants will be identified through the Neonatal Care Unit by the clinical care team based on clearly defined eligibility criteria. This approach ensures that participants meet specific gestational, medical, and family language background requirements relevant to the research question.
- Full-term infants will be recruited through the Oxford Brookes BabyLab participant database, which includes families who have previously expressed interest in taking part in developmental research. Infants will be selected to match the preterm groups on key demographic variables such as age, gender, and socioeconomic background.

This sampling approach is justified by the study's developmental and theoretical framework, which requires carefully defined comparison groups to isolate the effects of early auditory experience on language development. Random sampling is neither feasible nor appropriate in this context, as the study focuses on specific infant populations with well-defined characteristics.

### **5.3 Recruitment**

Eligible preterm infants will be identified by members of the direct clinical care team within participating NCUs through routine review of medical records. A research nurse will make the initial approach to families to assess interest in participation. Families who express interest will then be approached by a trained postgraduate research assistant at a suitable time to provide full study information and seek informed consent.

Full-term infants, and potentially preterm infants receiving standard care, will be recruited via the Oxford Brookes BabyLab database. Families registered in the database have previously consented to be contacted about research opportunities. Eligible families will be contacted when their child reaches the appropriate age and will be provided with full study information before deciding whether to take part.

Posters and flyers inviting families to join the Babylab Participant Database will be displayed across the hospital (e.g. maternity wards, lifts). The postgraduate research assistant will also spend some time in the ultrasound unit, where women/partners are waiting for their scans and talk about the study. At this point, parents will receive a flyer and interested parents will be asked to complete an expression of interest card to join the BabyLab Participant Database.

**SHORT TITLE/ACRONYM**

All recruitment procedures are designed to minimise burden, respect confidentiality, and ensure that participation is entirely voluntary.

**5.3.1 Sample identification**

**Preterm infants (womb-like environment group)**

Eligible preterm infants will be identified within participating Neonatal Care Units (NCUs). Identification will be carried out exclusively by members of the infant's direct clinical care team (e.g. neonatal research nurses or clinical staff), who will have legitimate access to medical records as part of their routine clinical role. The clinical team will screen infants against the study inclusion and exclusion criteria using existing medical records. No member of the research team will access identifiable medical records prior to consent.

For families identified as potentially eligible, the initial approach will be made by a neonatal research nurse or another appropriate member of the clinical care team. This first contact will be limited to providing brief, non-coercive information about the study and asking whether the family would be interested in hearing more. Families who express interest will then be referred to the research team. At a later, suitable time, a postgraduate research assistant from the project team will provide full study information and seek informed consent.

**Preterm infants (standard care group)**

The clinical care team will identify and approach families with babies who meet the eligibility criteria. They will provide brief verbal information about the study and distribute a written invitation letter and participant information leaflet. Families who are interested in learning more will be invited to complete an expression-of-interest card. These cards will be stored securely in a locked collection box at the nurse station. The research team will collect the cards regularly and follow up with families at a suitable time to provide full study details and seek informed consent.

**Full-term infants and potential standard-care preterm participants recruited outside NCUs**

Full-term infants, and potentially some preterm infants in the standard-care group, will be identified through the Oxford Brookes BabyLab participant database. This database consists of families who have proactively registered their interest in taking part in developmental research and have provided consent to be contacted about future studies.

Recruitment to the BabyLab database occurs via general publicity, including leaflets, posters, and the BabyLab website. These materials advertise participation in BabyLab research broadly rather than a specific study. Eligible families are contacted by email when their child reaches the appropriate age and are then provided with full written and verbal information about the study before any consent is sought.

The researcher will also spend some time in the ultrasound unit where women/partners are waiting for their scans and talk about the study. At this point, parents will receive a flyer and interested parents will be asked to complete an expression of interest card to join the BabyLab Participant Database.

**Publicity and resources**

**SHORT TITLE/ACRONYM**

Publicity materials (posters and leaflets) may be used to support recruitment to the BabyLab database and, where appropriate, to raise awareness of research opportunities for families of preterm infants. A study-specific poster will be developed for preterm populations.

**Confidentiality and data access**

Prior to consent, identifiable personal information and medical records will only be accessed by the infant's direct clinical care team. The research team will only receive contact details and participant-provided data after families have given informed consent. No Patient Identification Centres (PICs) will be used beyond the participating NCUs.

**Payments and expenses**

Participants will receive a voucher and a small token of appreciation for taking part. At each visit to the BabyLab, infants will receive a small toy or book. To compensate for parents' time and travel expenses, families will receive a £20 voucher per visit. These incentives are intended to offset expenses and time commitment and are not contingent on completion of all study visits.

**5.3.2 Consent**

Informed consent will be obtained prior to participants undertaking any activities that are specifically for the purposes of this study.

For preterm infants, the identification of potentially eligible families will be carried out by members of the infant's direct clinical care team within the Newborn Care Services. Given that parents of preterm infants may be in a particularly stressful situation, the initial approach will be made sensitively by a clinical or research nurse who is known to the unit. Families will be provided with brief verbal information about the study and asked whether they would be interested in hearing more. No research activities will take place at this stage.

Families who express interest will then be approached by a trained postgraduate research assistant or a member of the research team at a time deemed appropriate by the clinical team and the parents. The researcher will provide the approved written Participant Information Sheet and explain the purpose, procedures, potential risks and burdens, and potential benefits of the study in clear, non-technical language. Parents will be given the opportunity to ask questions and sufficient time to consider their participation before making a decision. Written informed consent will be obtained from a person with parental responsibility before any study-specific procedures begin.

For full-term infants recruited via the Brookes BabyLab database, families will be contacted by email with full written information about the study, including the Participant Information Sheet and consent materials. Families will be able to take as much time as they wish to review the information and ask questions by email or telephone before deciding whether to participate. Written informed consent will be obtained prior to any testing visit.

Consent discussions will be conducted by members of the research team who are knowledgeable about the study and trained in ethical research practice. Consent will be treated as an ongoing process, and parents will be reminded that participation is entirely voluntary and that they are free to

**SHORT TITLE/ACRONYM**

withdraw their child from the study at any time without giving a reason and without any impact on their child's clinical care or relationship with the hospital or university.

As participants are infants, consent will be obtained from parents or legal guardians with parental responsibility. The research does not seek assent from children, as they are below an age at which they can meaningfully provide informed consent. Capacity to consent will therefore rest solely with the parent or legal guardian, and researchers will ensure that consent is freely given, informed, and not influenced by perceived pressure from clinical or research staff.

All consent procedures and documentation will comply with REC approval, local regulatory requirements, and relevant legal and ethical guidelines.

## **6 ETHICAL AND REGULATORY CONSIDERATIONS**

This study has been designed in accordance with the principles of the UK Policy Framework for Health and Social Care Research, the Declaration of Helsinki, the General Data Protection Regulation (GDPR), and relevant Health Research Authority (HRA) guidance. The research methods are non-invasive, pose minimal risk, and are appropriate for the vulnerable population involved. The study aims to maximise potential benefits while minimising any risks or burdens to participants and their families.

### **Informed Consent**

Caregivers will be fully informed about the nature, purpose, procedures, and expected duration of the study through an approved written participant information sheet. This will be supplemented by verbal explanation from a trained member of the research team, with opportunities to ask questions and seek clarification. Written informed consent will be obtained from a person with parental responsibility before any research-specific activities take place.

Consent will be sought in a manner that recognises the emotional demands placed on families, particularly those with infants in neonatal care. Parents will be given sufficient time to consider participation, and consent will be treated as an ongoing process rather than a single event.

### **Voluntary Participation and Right to Withdraw**

Participation is entirely voluntary and free from coercion. Caregivers will be informed that they may withdraw their child from the study at any time, without providing a reason and without any impact on their child's care. If withdrawal occurs, no further data will be collected. Where requested, all data collected up to that point will be destroyed and not used in analyses.

**SHORT TITLE/ACRONYM**

**Risks, Burdens, and Safeguards**

The research procedures involve brief behavioural tasks, parental questionnaires, and audio/video recordings used solely for monitoring infant attention and task engagement. These procedures pose no physical risk and are comparable to activities infants experience in everyday interactions.

Given the vulnerability of preterm infants and the emotional strain experienced by parents in Neonatal Care Units (NCUs), particular care will be taken to minimise distress. Initial approaches to families of preterm infants will be made only by trained research nurses who are part of the clinical care environment, ensuring that families are approached sensitively and at appropriate times. Testing sessions will be paused or terminated immediately if an infant shows signs of distress or fatigue.

All members of the research team involved in direct contact with infants will hold valid DBS clearance and will be trained in infant testing procedures. The Principal Investigator has over seventeen years of experience conducting infant research and will oversee all procedures.

**Confidentiality and Data Protection**

All personal data will be handled in accordance with GDPR and the Data Protection Act. Identifiable information (e.g., consent forms and demographic questionnaires) will be stored securely and separately from research data. Research datasets will be pseudonymised using participant ID codes.

Audio recordings provided by parents will undergo destructive filtering to remove identifying content not required for the study. Raw audio files will be deleted once processing is complete. Video recordings of infants will be used only for monitoring task engagement and will not be used for dissemination or shared outside the research team.

No identifiable data will be included in publications, presentations, or public reports. Only fully anonymised, group-level data will be disseminated.

**Data Archiving and Open Research**

In line with open research practices, fully anonymised datasets will be archived at the end of the project and made publicly available via an approved data repository (e.g., the UK Data Service).

**SHORT TITLE/ACRONYM**

Participant information sheets will clearly state this intention. Archived data will contain no personal identifiers and will be used exclusively for academic research purposes.

**Dignity and Respect for Participants**

All research activities are designed to uphold the dignity, privacy, and welfare of infants and their families. Sessions will be scheduled flexibly to accommodate families' needs, with frequent breaks and a parent present at all times. The study does not interfere with routine clinical care, and all procedures have been developed in close consultation with neonatal clinicians and parent advisors to ensure acceptability and appropriateness.

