#### **Testing Intervals:**

Infants will be tested at 7.5, 9, 10.5, and 12 months (see Fig. 2), as delays are detectable at these ages. This longitudinal design will highlight pathways of early speech perception, crucial for studying atypical development.

[figure not shown]

Fig. 2. Summary of testing points.

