**SHORT TITLE/ACRONYM**

**Predictions:** Based on previous findings Preterm groups are expected to show delayed acquisition of these properties compared to the full-term group. If, as predicted, the delay stems from a lack of prenatal prosody exposure, the delay will appear in the Standard-Care-group but not in the Womb-Simulated-group.

**Analyses:** Data on looking times, vocabulary, and cognitive development will be collected and compared across the three study groups. Analyses will be conducted using linear mixed-effects models, which are particularly suitable for handling missing data in longitudinal studies with repeated measurements.

Analyses will be conducted using R and the lme4 package to fit linear mixed-effects models. Fixed effects will include Group (womb-simulated preterm, standard-care preterm, full-term), Age (7.5, 9, 10.5, 12 months), and Stimulus Type (e.g., alternating vs. non-alternating). Participants and stimuli will be included as random effects. Model selection will follow a stepwise comparison approach, retaining the model with the lowest BIC and a significant log-likelihood ratio test. A typical model will take the form:

`lmer(TotalLook~Group*Age*StimType+(Age|SubjectID)+(1|Stimulus)).`

P-values will be derived from F-values using the Satterthwaite approximation. Planned comparisons will use orthogonal contrasts. While SES, gestational age, and birth weight will not be included in the primary models, their effects will be explored in secondary analyses. All analyses will be pre-registered and conducted in line with open science practices.

Data will be summarised using descriptive statistics and visualised with graphs to illustrate group differences and developmental trajectories. Demographic matching of full-term infants will further strengthen causal inference by reducing potential confounding factors.

**Dissemination Activities:** Co-designed resources such as infographics, videos, animations, and a website will target families and practitioners. Workshops for families, practitioners, and

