**10.2 Appendix 2 – Schedule of Procedures (Example)**

Procedures	Visits (insert visit numbers as appropriate)							
	Identification	Screening	Recordings	Womb-like exposure	7.5m	9m	10.5m	12m
1. Identification and initial approach to families	x							
2. Informed consent		x						
3. Audio recording of parental speech (womb-like acoustic environment exposed group only)			x					
4. Exposure to womb-like acoustic environment (womb-like acoustic environment exposed group only)				x				
5. Language and developmental assessments					x	x	x	x
6. Parent questionnaires (vocabulary measures and demographics)					x	x	x	x
7. Cognitive development assessment					x			x

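### Age enters the model as its four target values, with no term for age at test and no visit tolerance, so a systematic group difference in lateness would bias the group contrasts

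*Protocol*

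**What the plan says.** Protocol section 3, Testing Intervals: "Infants will be tested at 7.5, 9, 10.5, and 12 months". Neither that section nor the schedule in Appendix 2 (10.2) says how far a visit may fall from its target age.

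Protocol section 3, Analyses, lists among the fixed effects "Age (7.5, 9, 10.5, 12 months), and Stimulus Type" and gives as the typical model "lmer(TotalLook~Group*Age*StimType+(Age|SubjectID)+(1|Stimulus" (closing brackets omitted). No term for age at test appears. Gestational age, birth weight and SES are kept for secondary analyses. Pre-registration of all analyses is announced.

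Protocol section 6, Dignity and Respect for Participants: "Sessions will be scheduled flexibly to accommodate" families' needs; the same sentence goes on to breaks and the parent's presence.

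On entry to the study:
- **Womb-simulated families** are enrolled while the infant is in the neonatal unit.
- **Standard-care preterm infants** are recruited by the same strategy but are, where possible, infants already discharged (section 3, Participants). Some may come from the BabyLab database.
- **Database families** are approached by age: "Eligible families are contacted by email when their child reaches the appropriate age" (section 5.3.1). Full-term families may then take as long as they like before consenting, and consent must precede any visit (section 5.3.2).
- **Full-term infants** are matched to the preterm groups on age, among other variables, with no tolerance given (section 5.2.2).

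**The concern.** As written, the model treats all infants at a given visit as the same age. Visits are 1.5 months apart, so a delay of a few weeks is a sizeable part of the interval. The protocol itself expects the outcomes to move over this period: sensitivity to native stress is said to grow, sensitivity to non-native tone to decline, and vocabulary is tracked at every visit. A group tested later would therefore look more mature on each of these.

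Allocation is not random, so nothing in the design makes lateness equal across groups. A systematic difference would enter the terms that carry the main prediction, which is a delay under standard care but not with womb-like exposure. Depending on its direction, it could create, enlarge or hide that contrast.

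**Working it through.** **Inputs from the protocol.** Forty infants per group, 20% attrition, alpha 0.05, planning effects d = 0.59 to 0.80 (section 3, Participants, and section 5.2.1).

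**The plan's own figure.** 3 × 40 = 120, and 120 / (1 − 0.20) = 150. The stated total reproduces and is not in dispute. At 40 per group and d = 0.59, a two-sided t-test has power 0.74; this is the baseline used below.

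**Assumed inputs (not in the documents).** Change with age s = 0.1 to 0.4 SD per month; difference in mean lateness w = 1 to 4 weeks; 4.345 weeks per month.

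**Where the bias goes.** Write the outcome as a + s × (nominal age + lateness). If one group is later by L months on average at every visit, its mean shifts by s × L at every visit. That shift lands in Group. For looking times, where the effect of interest is the difference between stimulus types, s is the monthly change in that difference and the shift lands in Group by Stimulus Type. Because the shift is the same at each visit, the interaction with Age does not move. That last result needs both a constant lag and linear change.

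**Size of the shift.** Spurious d = s × w / 4.345.
- Smallest: 0.1 × 1 / 4.345 = 0.023, and 0.023 / 0.59 = 4%.
- Middle: 0.2 × 4 / 4.345 = 0.184, and 0.184 / 0.59 = 31%.
- Largest: 0.4 × 4 / 4.345 = 0.368, and 0.368 / 0.59 = 62%.

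**Effect on a single-visit comparison of two groups of 40.** Non-central t with 78 degrees of freedom and non-centrality d × √(40/2).

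| Spurious d | Two-sided false-positive rate | Power for a true 0.59 if the shift opposes it (d = 0.59 − shift) |
|---|---|---|
| 0 | 0.05 | 0.74 |
| 0.023 | 0.051 | 0.71 |
| 0.092 | 0.069 | 0.60 |
| 0.184 | 0.13 | 0.43 |
| 0.368 | 0.37 | 0.17 |

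**Equal lateness.** The bias is s × 0 = 0. A scatter of 0.5 month (assumed) raises the SD by a factor √(1 + (0.5s)²). This is √1.0025 = 1.001 at s = 0.1 and √1.04 = 1.020 at s = 0.4, an increase of 0.1% to 2%.

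**Does exact age remove the bias?** Simulation: two groups of 40, four visits, no true group effect, random intercept SD 0.6, residual SD 0.8 (total SD 1), linear change, 150 runs per case. Each cell gives the mean group effect, then the false-positive rate.

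| Lag (months) | s | Nominal age | Actual age |
|---|---|---|---|
| 0 | 0.2 | −0.01; 0.06 | −0.01; 0.05 |
| 0 | 0.4 | −0.02; 0.04 | −0.01; 0.04 |
| 0.5 | 0.2 | 0.11; 0.12 | 0.01; 0.05 |
| 0.5 | 0.4 | 0.20; 0.27 | 0.00; 0.08 |
| 1.0 | 0.2 | 0.22; 0.25 | 0.02; 0.04 |
| 1.0 | 0.4 | 0.39; 0.67 | −0.01; 0.05 |

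The Monte Carlo standard error at a rate of 0.05 is √(0.05 × 0.95 / 150) = 0.018, so the rates are approximate. The simulation has one score per visit and no stimulus factor. It shows the mechanism and its cure, not the operating characteristics of the full planned model.

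**The case against.** Visit windows and the coding of age are often settled in an analysis plan or pre-registration, and the formula is offered only as typical. The list of four ages could simply name the design points. The protocol does not say whether Age is a factor or numeric, nor that exact age will be ignored. This part stands as a caution. Even so, the protocol goes beyond silence: it states the Age effect by target values and prints a model without age at test, and a better choice costs almost nothing.

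Three stronger readings are tempting, and the documents do not support them.
- **That the flexible-scheduling sentence lets test ages drift.** It sits in a paragraph on dignity, beside breaks and parental presence, and may concern day and time only. The operative text says infants are tested at the four ages.
- **That one group will attend later.** Nothing says so. The two preterm groups are recruited largely by the same strategy, full-term infants are matched on age, and contacting database families by age is itself a form of age control. Late consent would mainly affect the first visit. What remains is that routes differ in part, the age matching has no tolerance, and it does not cover the contrast between the two preterm groups.
- **That any difference in lateness becomes a language effect.** Bias needs systematic differential lateness and an outcome that changes over weeks. Cognitive scores would be largely protected if age-normed; the protocol does not say which score is used.

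**Conclusion.** The point holds as a conditional weakness with a cheap remedy. The stated model has no term for age at test and no visit tolerance is set, so systematic differential lateness would pass into the Group and Group by Stimulus Type terms and the vocabulary contrasts. Under the assumed ranges the shift is d = 0.02 to 0.37. It is negligible to small for a one-week difference (0.02 to 0.09) and material for four weeks at the faster rates of change. It is zero if lateness is equal. These sizes rest wholly on assumed rates and lags and are not a forecast for this trial.

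Whether the test ages are chronological or corrected is a separate and larger gap. Against an assumed 40-week term, the two scales differ by (40 − 34) / 4.345 = 1.4 to (40 − 26) / 4.345 = 3.2 months for eligible preterm infants. The present point arises on either scale.

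**What to change.** In Protocol section 3, Analyses, do one of the following:
1. Keep the four-level visit factor and add actual minus nominal age at test as a covariate, with its interaction with Stimulus Type in the looking-time models.
2. Enter exact age at test as a continuous term, with curvature if needed, and estimate the group contrasts at 7.5, 9, 10.5 and 12 months.

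Define age on whichever scale, chronological or corrected, the study adopts. State a tolerance around each target age in Testing Intervals, and keep late visits in the analysis at their true age. Report mean age at test by group and visit, so that readers can see whether lateness differed.

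**Cost.** A few lines of text, with no extra infants or visits. The dates of birth and testing (and the due date, if age is corrected) must be recorded; the protocol does not list them as collected data, although scheduling by age implies that birth dates are known. The first option costs one extra term, plus its interaction for looking times, and assumes smooth change with age within each visit. The second assumes a smooth age curve across visits.
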